10.7 Analysis of Minnesota Impulsive Disorders Interview (MIDI)

The Minnesota Impulsive Disorders Interview (MIDI) will be administered to monitor for the development of intense impulsive behavior. It includes the following modules: buying disorder, kleptomania, trichotillomania, intermittent explosive disorder,

pyromania, pathological gambling and compulsive sexual behavior. A subject's MIDI screen is positive for a module if:

- Buying Disorder: Positive screen if the subject answers "yes" to 1a, 2a, 3a, and 4a
- Kleptomania: Positive screen if the subject answers "yes" to 1a, 2a, 3a, and 4a
- Trichotillomania: Positive screen if the subject answers "yes" to 1, 3, 4a, 5, and 6
- Intermittent Explosive Disorder: Positive screen if the subject answers "yes" to 1a, 1b, 1c, and 1d; in addition, the subject must answer "no" to 1f
- Pyromania: Positive screen if the subject answers "yes" to 1a, 2, 3, 4, and 5; in addition, the subject must answer "no" to 1b, 1c, 1d, and 1e
- Pathological Gambling: Positive screen if the subject answers "yes" to 1, and to at least 5 of the rest of the questions
- Compulsive Sexual Behavior: Positive screen if the subject answers "yes" to 1, 2a, 3a, or 4a

Positive screens on the MIDI will be summarized for the study period on or before the date of randomization and during the 12-week Treatment Period. Each summary will include the number and percentage of subjects in each treatment group with a positive screen for each MIDI module as well as for any of the MIDI modules.

A summary of the number and percentage of subjects with a positive screen for each MIDI module as well as for any of the MIDI modules during the Transition Period will also be provided for LCIG subjects who enter the Transition Period.

A listing will also be prepared that includes all subjects with 1 or more positive screens for any of the MIDI modules.

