For all females of childbearing potential a serum pregnancy test will be performed at V1 and Premature Discontinuation/End of Study. A negative urine pregnancy test result is required to be done by the site prior to the NJ and/or PEG-J placement procedure and/or any radiological procedures. Additional testing may be required per local regulations.

Minnesota Impulsive Disorders Interview (MIDI)

To monitor for development of intense impulsive behavior, the Minnesota Impulsive Disorders Interview (MIDI)²⁹ will be administered at the times indicated in Table 4 or whenever relevant symptoms emerge. If the subject's impulsivity during the Screening Period is judged to be clinically significant in the judgment of the Investigator, they will

be excluded from participation in the study and referred for appropriate follow-up care. Any subject noted to have intense impulsive behavior during the study as assessed by the MIDI, or via clinical interview, will be evaluated immediately by the Investigator. The AbbVie TA MD should also be notified. The MIDI will be administered as indicated in Table 4.

Columbia-Suicide Severity Rating Scale (C-SSRS)

The Columbia-Suicide Severity Rating Scale (C-SSRS)³⁰ is a systematically administered instrument designed to assess suicidal behavior and ideation, track and assess all suicidal events, as well as the lethality of attempts. Additional features assessed include frequency, duration, controllability, reason for ideation, and deterrents. The C-SSRS is considered a low-burden instrument as it takes less than 5 minutes to administer.

Any subject noted to have suicidal ideation with plan within the last year, either via answering "yes" to question 4 and/or question 5 to the suicidal ideation portion of the C-SSRS, or via clinical interview, will be evaluated immediately by the Investigator. The AbbVie TA MD will also be notified. In addition, if the subject expresses suicidal ideation at any time during the study, the Investigator should be immediately notified as well as the AbbVie TA MD.

Under no circumstances should a subject who has positively endorsed or expressed suicidal ideation be left alone, be allowed to exit the site, or go home before a qualified medical professional has evaluated the subject's risk.

The "Baseline/Screening" C-SSRS will be the first assessment scale administered to the subject. At each subsequent visit, the "Since Last Visit" C-SSRS scale should be administered.

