8.1.4.4 Vital Sign Variables and Weight

For each vital sign and weight variable, analyses of the mean change from baseline to each scheduled visit and to the final value will be presented by treatment group and for both treatment groups combined. For this analysis, the average of multiple observations on the same day will be calculated and treated as the observation for the day.

Criteria for potentially clinically significant (PCS) values for selected vital sign and weight variables will be pre-specified in an SAP prior to database lock. For each variable, a summary of the number and percentage of subjects who have at least one post-baseline observation that meets the PCS criteria and is more extreme than their baseline value will be provided.

8.1.4.5 **ECG Variables**

For each ECG variable, analyses of the mean change from baseline to each scheduled visit and to the final value will be presented by treatment group and for both treatment groups combined. For this analysis, the average of multiple observations on the same day will be calculated and treated as the observation for the day.

Criteria for potentially clinically significant (PCS) values for selected ECG variables will be pre-specified in an SAP prior to database lock. For each variable, a summary of the number and percentage of subjects who have at least one post-baseline observation that meets the PCS criteria and is more extreme than their baseline value will be provided for each treatment group and for both treatment groups combined.

8.1.4.6 **Additional Safety Variables**

The following additional summaries of safety measures will be prepared.

- The number of subjects with 1 or more positive screens on a Minnesota Impulsive Disorders Interview (MIDI) module at baseline as well as during the treatment period, and
- The number of subjects with 1 or more affirmative responses to the Columbia Suicide Severity Rating Scale (C-SSRS) at baseline as well as during the treatment period.

8.1.5 **Interim Analysis**

No interim analysis is planned for this study.

8.2 **Determination of Sample Size**

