10.3.3 Potentially Clinically Significant (PCS) Laboratory Values

Criteria for potentially clinically significant (PCS) values have been predefined for selected laboratory variables as outlined in Appendix C. For each variable, a summary of the number and percentage of subjects in each treatment group who have at least one post-baseline observation during the 12-week Treatment Period that meets the PCS criteria and is more extreme than their baseline value will be provided.

A summary of the number and percentage of subjects who have at least one observation during the Transition Period that meets the PCS criteria and is more extreme than their baseline value will be provided for LCIG subjects who enter the Transition Period.

A listing will also be prepared that will include, for each variable, all observations for each subject that met the PCS criteria for that variable at any time during the study. No comparisons of treatment groups will be performed.

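### SAP 10.7 plans no by-arm count of new-onset positive MIDI screens, although the interview is there to monitor for impulsive behaviour that develops on study

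*SAP*

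**What the plan says.** SAP 10.7 gives the purpose of the MIDI: it "will be administered to monitor for the development of intense impulsive behavior". It defines a positive screen for each of seven modules and then plans three outputs for the main study period.

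- A summary for the time up to randomisation and another for the treatment period: "Positive screens on the MIDI will be summarized for the study period on or before the date of randomization and during the 12-week Treatment" Period.
- The content of both: "Each summary will include the number and percentage of subjects in each treatment group with a positive screen for each MIDI module", and likewise for any module.
- A subject listing: "A listing will also be prepared that includes all subjects with 1 or more positive screens for any of the MIDI modules". Its columns are not specified.

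Protocol 8.1.4.6 plans the same two-period count of subjects with a positive "module at baseline as well as during the treatment period". Neither document makes the second count conditional on the first, and neither plans a shift table for the MIDI.

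Entry does not require a negative MIDI. In the MIDI part of Protocol 5.3.1.1 the exclusion applies "If the subject's impulsivity during the Screening Period is judged to be clinically significant in the judgment of the Investigator". Exclusion criterion 10 likewise turns on clinical significance, over the three months before Screening.

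**The concern.** The stated aim is to detect development, which means onset after treatment starts. A subject who was positive at screening, was not judged clinically significant, and is positive again at Week 4 counts in the treatment-period table exactly as a new case does.

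Carry-over of this kind is possible on the documents' text. SAP 10.6 and 10.8 state that after Visit 1 the sleep-attack questions and the C-SSRS ask about experience since the last visit. No recall period is stated for the MIDI. The Compulsive Sexual Behavior module, as SAP 10.7 words it, is positive on a single affirmative answer.

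Impulse control disorders are among the important identified risks in Protocol 3.2. They are not an adverse event of special interest (Protocol 6.2.3, SAP 10.2.3), so no dedicated adverse event summary covers them. The MIDI is the only impulsivity instrument in the schedule of activities. What is at stake is whether the report can state, by arm, how many subjects became positive.

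**Working it through.** The plan contains no MIDI figure to reproduce. The check is whether the two planned counts determine the number of new cases.

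**Inputs.** For one arm and one module, let N be the subjects in the arm, B those positive on or before randomisation, and T those positive during the 12-week period. SAP 10.7 tabulates B and T. N = 30 is an assumption, from about 60 subjects randomised 1:1 (Protocol 8.2); the safety dataset may be slightly smaller in the LCIG arm.

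**Formula.** Let x be the new-onset count: positive on treatment and negative before. The persisting count is T − x, and it lies between 0 and B. Also, x cannot exceed the N − B subjects who were negative at entry. Hence

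max(0, T − B) ≤ x ≤ min(T, N − B).

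**Results with N = 30.**

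| B | T | Lower bound | Upper bound | New onset |
|---|---|---|---|---|
| 0 | 3 | max(0, 3) = 3 | min(3, 30) = 3 | exactly 3 |
| 1 | 3 | max(0, 2) = 2 | min(3, 29) = 3 | 2 to 3 |
| 2 | 5 | max(0, 3) = 3 | min(5, 28) = 5 | 3 to 5 |
| 3 | 3 | max(0, 0) = 0 | min(3, 27) = 3 | 0 to 3 |
| 5 | 5 | max(0, 0) = 0 | min(5, 25) = 5 | 0 to 5 |

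Apart from the extreme case of a whole arm being positive, x is fixed only when B = 0 or T = 0. If both arms printed B = 3 and T = 3, the tables would look identical, yet the between-arm difference in new cases could lie anywhere from 0 − 3 = −3 to 3 − 0 = +3.

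**How many subjects this touches.** Expected B per arm is 30 × prevalence. The documents give no prevalence, so these values are assumptions:

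- 0%: B = 0, and the planned count already equals new onset.
- 2%: 30 × 0.02 = 0.6 per arm. Chance of at least one positive among 60: 1 − 0.98^60 = 70%.
- 5%: 30 × 0.05 = 1.5 per arm. Chance of at least one among 60: 1 − 0.95^60 = 95%.

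**Comparison within the SAP.** Laboratory shift summaries (10.3.2) count subjects who were not high at baseline and become high, and likewise for low. Summaries of potentially clinically significant values (10.3.3, 10.4.3, 10.5.2) count a subject only if the value "meets the PCS criteria and is more extreme than their baseline value". The MIDI has no rule of either kind.

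**The case against.** The strongest reply is that new cases will be visible anyway, and much of it stands.

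- **The listing.** A reader might infer that new cases go unreported. The documents do not support that. Every subject with a positive screen is to be listed, and with about 60 subjects new cases could be picked out by hand if the listing shows module and visit. But its columns are unspecified, and a listing gives no count or percentage by arm.
- **Adverse events.** Developing clinically significant impulsive behaviour is among the adverse events requiring discontinuation (Protocol 5.4.1). Treatment-emergent events are defined by onset and compared between arms (SAP 10.2, 10.2.2). This covers the cases judged clinically significant; a structured screen is useful for what falls outside that judgement.
- **Repeated counting.** A reader might infer that an old positive is counted again at each visit. It is not: the table counts subjects, once per period. Nor does silence on recall show that the MIDI asks about lifetime behaviour, or that every early positive persists.
- **Large dilution or hidden imbalance.** Assuming 10–30% positive at entry would give 30 × 0.10 = 3 to 30 × 0.30 = 9 per arm. Nothing in the documents supports that range, and the entry criteria push prevalence down. Six of the seven modules also need several answers together. A chance imbalance at entry would show in the planned pre-randomisation table by arm.
- **Comparators.** The rule for potentially clinically significant values is not strictly a new-onset rule, since a subject already abnormal can worsen and count. The sleep-attack and C-SSRS summaries use the same before-and-after layout as the MIDI. They do, however, have a stated recall since the last visit, which limits carry-over; for that reason the point should not be extended to the C-SSRS.

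**Conclusion.** The point holds as a reporting gap in a descriptive safety summary. No by-arm count of new-onset positive MIDI screens is planned, and the two planned counts generally only bound it. This rests on two readings of the text: the treatment-period count is unconditional, and a MIDI-positive subject may be randomised.

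The practical size rests on a baseline prevalence that the documents do not give. It is nil if no one is positive before randomisation, and about 0.6–1.5 subjects per arm at an assumed 2–5% with 30 per arm. The case for the change is that it matches the table to the instrument's stated purpose. It would not make a trial of this size able to test a difference in impulsivity. The primary and secondary efficacy analyses are unaffected.

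**What to change.** In SAP 10.7, add for each module and for any module, by arm:

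1. **New onset:** number and percentage of subjects positive during the 12-week Treatment Period among those negative on that module (or on all modules, for the any-module row) at every MIDI done on or before randomisation.
2. **Persisting:** subjects positive in both periods, in a separate row.

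A shift table from pre-randomisation to on-treatment status would serve equally well. Also specify that the listing shows module and visit.

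The cost is a few lines of SAP text and programming. The MIDI is already scheduled at Visits 1 and 3, at Visit 2 if held, and at Weeks 2, 4, 8 and 12, so no data are added. The one drawback is a slightly smaller denominator for the new-onset row, for example 30 − 3 = 27 if three subjects in an arm were positive at entry. The two planned counts can stay, which keeps the table consistent with Protocol 8.1.4.6.

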10.8 Analysis of Columbia-Suicide Severity Rating Scale (C-SSRS)

The Columbia-Suicide Severity Rating Scale (C-SSRS) is a systematically administered instrument developed to track suicidal adverse events across a treatment study. At Screening Visit 1 the C-SSRS will be administered to collect lifetime history as well as experience during the past year. At all other visits, the C-SSRS will collect experience since the last visit. Affirmative responses on the C-SSRS will be summarized for the following study periods and reporting timeframes: Screening: Lifetime and Past year; before randomization: Since last visit; and on or after Day 1: Since last visit.

Each summary will include the number and percentage of subjects in each treatment group with one or more affirmative responses to each of the 5 suicidal ideation questions, each of the 6 suicidal behavior questions, any of the 5 suicidal ideation questions, any of the 6 suicidal behavior questions, any suicidal ideation or behavior question, and the non-suicidal self-injurious behavior question during the 12-week Treatment Period. No comparisons of treatment groups will be performed.

A summary of the number and percentage of subjects with one or more affirmative responses to the questions listed above during the Transition Period will also be provided for LCIG subjects who enter the Transition Period.

A listing will also be prepared that includes all subjects with 1 or more affirmative responses.

11.0 Special Statistical Topics

There are no special statistical issues to be described or addressed.

12.0 Summary of Changes

This SAP contains no change in analysis from the latest version of the protocol (Protocol Amendment 1).

13.0 Appendices

Appendix A. Study Activities

		OMT/LCIG	U	LCIG Treatment	tment	0	MT/LO	JG Tr	OMT/LCIG Treatment	LCIG 1	LCIG Treatment
	171	671	6/1	VI NT/BEC 1		V5 WIE	7V6 1/11	ΥT	170	V9 W1-12	Transition to
Activity	v1 Screening	v 2 Screening	v.5 Randomization	Placement D1	Visits	2 WK	4 4	% X X	vo Wk 12/ET	WK 15 FU ^a	Unmercial Visits ^b
Visit Number for	V1	V2 ^c	V3	$V4^{d}$		V5	9A	LΛ	V8	61	Every 6 and
UMT/LCIG Informed Concent ^e	>	(Optional)									12 Weeks
Intormed Consent Medical/Neurological/PD	x x		X ^f								
History											
Concomitant Medication (including anti-PD and Dyskinesia medications)	Х	Х	Х	Х	X	Х	Х	Х	Х	X	Х
Anti-PD Medication History	Х										
Physical Examination ^g	Х	Х	Х	Х		Х	Х	Х	Х	Х	
Neurological Exam	Х	Х	Х			Х	Х	Х	Х	Х	
Dermatological Exam ^g	Х								Х		
GI Exam ^g	Х								Х		
NJ or PEG-J decision	Х										
Nasojejunal Tube Placement/Titration ^h (Optional)				Х							
PEG-J Placement Procedure ^h				Х							

48

		OMT/LCIG		LCIG Treatment	tment)MT/L(JIG Tre	OMT/LCIG Treatment	LCIG	LCIG Treatment
	V1	٢٨	۲٩	V4 NI/PEC-I	Titration	V5 VI	V6 Wk	V7 Wk	87	V9 We 13	Transition to Commercial
Activity	Screening	Screening	Randomization	Placement D1	Visits	2	4	8	Wk 12/ET	FU ^a	Visits ^b
Radiological Check of Tube Placement ⁱ				Х							
PEG-J Site (Stoma) Check				X	X					Х	
Vital Signs/Weight	Х		Х	Х	Х	Х	Х	Х	Х	Х	X
Height	Х										
ECG	Х							Х	Х		
Clinical Labs	X^k		\mathbf{X}^{k}					х	Х		
Urine Drug/Alcohol Screen	Х										
Special Laboratory Tests ¹	Х		Х				 	Х	Х		X
Pregnancy Test ^m	Х			Х					Х		
Adverse Events	Х	Х	Х	Х	Х	Х	Х	Х	Х	Х	X
Product Complaints				Х	Х	Х	Х	Х	Х	Х	X
Dose Titration Diary ⁿ				Х	Х						
Subject Dosing Diary Completion ^o					Х	Х	Х	Х	Х		
PD Diary training and concordance evaluation	Х										
PD Diary ^o			Х			Х	Х	Х	Х		

49

		OMT/LCI	CIG	LCIG Treatment	utment	0)MT/L(CIG Tre	OMT/LCIG Treatment	FCIG	LCIG Treatment
						V5	9A	LΛ		67	Transition to
Activity	V1 Screening	V2 Screening	V3 Randomization	V4 NJ/PEG-J Placement D1	Titration Visits	2 Wk	4 4	% 8	V8 Wk 12/ET	Wk 13 FU ^a	Commercial Visits ^b
LCIG System and Pump Training (Subject and Caregiver)			Х	Х							
LCIG Titration ^p				X	х						
Study Drug Prescription Record (LCIG treatment group only)				Х	Х	Х	x	Х	Х	Х	
Removal of PEG-J ^a									Х		
LCIG Cassettes Dispensed				Х		Х	Х	Х	Х	Х	Х
LCIG Cassettes Returned						Х	Х	Х	Х	Х	Х
MMSE	Х										
Sleep Attacks Questionnaire ^q	Х	Х	Х			Х	Х	Х	Х	Х	
C-SSRS ^r	Х	Х	Х	X		Х	Х	Х	Х	Х	Х
MIDI	Х	Х	Х			x	x	x	Х	х	Х
UDysRS ^s			Х			Х	Х	Х	Х		
UPDRS II and III ^t	Х		Х			Х	Х	Х	Х		
mAIMS ^u			Х			Х	Х	Х	Х		
PDQ-8			Х					х	Х		
CGI-C						х	Х	х	Х		

50

		OMT/LCI	IG	LCIG Treatment	atment		MT/L	CIGTr	OMT/LCIG Treatment	LCIG	LCIG Treatment
	V1	V2	V3	V4 NJ/PEG-J	Titration	V5 Wk	V6 Wk	V7 Wk	V8 Tan 12	V9 Wk 13	Transition to Commercial
Acumiy CGI-S	ocreening	Screening	Kanuomizauon X		V ISIUS	4	4	¢	WK 12/E1	D	V ISIUS
King's PD Pain Scale			x				×	x	Х		
V = Visit; D = Day; FU = Follow-Up; Wk = Week	ollow-Up; Wk	= Week					1				
a. Applicable only to LCIG subjects who prematurely discontinue LCIG treatment, or complete LCIG study treatment but will not transition to commercial LCIG.	IG subjects who	o prematurely	discontinue LCIG trea	atment, or complet	te LCIG stud	y treatm	ent but	will not	transition to con	nmercial LC	IG.
Applicable only to LCIG subjects who complete LCIG study treatment and will transition to commercial LCIG. Subjects will return every 6 weeks to return used LCIG cassettes and be dispensed cassettes. Safety assessments will be completed every 12 weeks until subjects' transition to commercial LCIG.	IG subjects who rsed cassettes.	o complete LC Safety assessm	IG study treatment ar tents will be complete	nd will transition to ad every 12 weeks	o commercial until subject:	LCIG. s' transit	Subjection to c	ts will re ommerc	sturn every 6 we ial LCIG.	eks to return	used LCIG
Visit 2 is optional and is based on the Investigator's discretion of individual subject need during stabilization of anti-PD medications and medications to treat dyskinesia.	is based on the	Investigator's	discretion of individu	al subject need du	ring stabiliza	tion of a	inti-PD	medicat	ions and medica	utions to treat	dyskinesia.
Visit 4 for LCIG Treatment (LCIG) group only.	ment (LCIG) gr	roup only.	•								
Study-related assessments, procedures or activities cannot occur prior to subject completing signed informed consent process.	ents, procedures	s or activities c	annot occur prior to s	subject completing	signed infor	med cor	isent pr	ocess.			
Update Medical/Neurological/PD History with any findings from Labs, Dermatologists, etc.	ological/PD His	tory with any i	tindings from Labs, L	ermatologists, etc.							
At Screening Visit 1 and Randomization Visit 3 a full physical examination will be performed. Symptom-driven physical examinations will be performed at subsequent visits. Prior to Visit 3, the Investigator and GI/surgeon or interventional radiologist, or their designated qualified personnel will thoroughly evaluate the subject's risk of undergoing PEG-J procedure. The dermatological exam will be performed prior to Visit 3 and Week 12/ET visit. If a suspicious lesion is present, a biopsy should be obtained for proper diagnosis and confirmation that lesion does not meet exclusion criteria before the subject is randomized.	nd Randomizati , the Investigato cedure. The del ienosis and conj	ion Visit 3 a fu r and GI/surge rmatological e firmation that	Ill physical examinations of the second of t	on will be perform adiologist, or theii id prior to Visit 3 z exclusion criteria F	r designated (and Week 12, acfore the sub	n-driver qualified /ET visit	l physic l person t. If a s' andomi	al exam nel will uspiciou zed.	inations will be thoroughly eval is lesion is prese	performed a luate the subj nt, a biopsy s	t subsequent ect's risk of should be
h. For subjects randomized to LCIG treatment, a temporary NJ tube may be used to optimize the dose of LCIG before treatment with a PEG-J is started. The NJ test phase should not last longer than 7 days. Following the NJ test phase, a PEG-J will be performed by a gastroenterologist proceduralist, surgeon or interventional radiologist.	ed to LCIG trea than 7 days. Fo	tment, a temport llowing the N.	orary NJ tube may be used to optimize the dose of LCIG before treatment with a PEG-J is started. The NJ test phase J test phase, a PEG-J will be performed by a gastroenterologist proceduralist, surgeon or interventional radiologist. Total	used to optimize t will be performed	he dose of L(by a gastroer	CIG beform Iterologi	ore treat ist proce	etment w eduralist	ith a PEG-J is st surgeon or inter	arted. The N srventional ra	IJ test phase adiologist. Tota
ume to turation via NJ and FEG-J should not exceed 14 days. Atternatively, subjects may proceed directly to placement of FEG-J II deemed appropriate by investigator. The number of days to titrate will vary for each subject.	the will vary for	each subject.	1 14 days. Auemauve	ery, suojects may F	oroceea alrec	uy to pr	acemen	1 OI FEC	r-J II acemea ap	ргорпаце ру	Invesugator. 11
LCIG treatment group only. Radiological check of NJ and PEG-J to determine correct location should occur prior to LCIG infusion initiation and prior to restart of LCIG post PEG-J placement. Additional checks can be done at any time during treatment if indicated for worsening of Parkinsonian symptoms not responsive to extra doses.	only. Radiolog Additional che	gical check of] scks can be do	NJ and PEG-J to deterne at any time during	rmine correct loca. treatment if indica	tion should o ated for wors	ccur pridential	or to LC ? Parkin	JIG infu sonian s	sion initiation any ymptoms not re-	nd prior to re sponsive to e	start of LCIG xtra doses.
j. PEG-J site, stoma check will be done within 24 hours of PEG-J placement and anytime from Day 2 to 7 post PEG-J.	ck will be done	within 24 hour	rs of PEG-J placemen	t and anytime fron	n Day 2 to 7	post PE(G-J.				
k. PT/PTT will be performed only at Screening Visit 1.	med only at Scr	eening Visit 1									

ð	Obvie Levodopa-Carbidopa Intestinal Gel (LCIG) M15-535 – Statistical Analysis Plan Version 1.0 – 21 May 2018
N.E. T. & C. C. B. M. A.	Special labs to detect vitamin deficiencies, listed in Table 5 in the protocol, will be performed at the times indicated in the Appendix A, Study Activities. If at any time during the study a subject displays symptoms of polyneuropathy, the Investigator must perform this lab panel and any other assessment that the Investigator feels is appropriate for the revealution of polyneuropathy. They other mergenancy test result is a commentary symptoms. Through terms are streaming Visit 1 only. There evolution of polyneuropathy and protom tests will be done at Screening Visit 1 only. The revealution of polyneuropathy symptoms. Thyroid thermoles of General Proceedures and any radio performant and the study exist in the bospital, the study statemets test in the bospital, the study statemet sectored to the NJ and or PEG-J placement procedure and any radiological procedures. While the subject is optimized and then one AM and once PM it will be completed until the subject so prime of the AJ and test and extra does until the subject is optimized. The Subject Dosing Diary and the Parkinson's Disease Diary will be completed until the subject so the 3 consecutive days prior to each visit. The Subject Dosing Diary and the Parkinson's Disease Diary will be completed until the subject so the 3 consecutive days prior to each visit. The Subject Dosing Diary and the Parkinson's Disease Diary will be completed until the subjects or their caregivers for the 3 consecutive days prior to each visit. The Subject Dosing Diary and the Parkinson's Disease Diary will be completed to the subject sorted and strat does until the study statemet context and any turtation data and the advect and scenared and the analyst and the subject sorted and the advect advect and strat does until the subject sorted and the advect advect and strat does until the subject and the advect advect advect advect advect advect and strat does until the subject. The study strated at this time through the the strates and the dose dystinestican Atta advect advect advect adve

Clinical Laboratory Tests	Very Low (VL)	Very High (VH)
Hematology		
Activated partial thromboplastin time	NA	> ULN
Hemoglobin	< 100 g/L (6.2 mmol/L)	> 40 g/L above ULN
Prothrombin Intl. Normalized Ratio	NA	> ULN
Leukocytes	$< 2 \times 10^{9}/L$	$> 100 \times 10^{9}/L$
Lymphocyte	$< 0.5 \times 10^{9}/L$	$> 20 \times 10^{9}/L$
Neutrophil	$< 1 \times 10^{9}/L$	NA
Platelets	$< 75 \times 10^{9}/L$	NA
Chemistry		
Bilirubin	NA	> 1.5 × ULN
Cholesterol	NA	> 12.92 mmol/L (500 mg/dL)
Creatinine	NA	> 1.5 × ULN
Calcium (corrected serum)	< 1.75 mmol/L (7.0 mg/dL)	> 3.1 mmol/L (12.5 mg/dL)
Glucose (fasting)	< 2.2 mmol/L (40 mg/dL)	> 13.9 mmol/L (250 mg/dL)
Potassium	< 3.0 mmol/L	> 6.0 mmol/L
Triglycerides	NA	> 5.7 mmol/L (500 mg/dL)
Urate	NA	> 590 umol/L (10 mg/dL)
Albumin	< 20 g/L	NA
Sodium	< 130 mmol/L	> 155 mmol/L
Phosphate	< 0.6 mmol/L (2.0 mg/dL)	NA
Enzymes		
Alanine aminotransferase (ALT)	NA	$> 3 \times ULN$
Alkaline phosphatase	NA	> 2.5 × ULN
Aspartate aminotransferase (AST)	NA	> 3 × ULN

